7.7.2 Permitted Treatments

Any medication or vaccine (including over-the-counter or prescription medicines, vitamins, and/or herbal supplements) that the participant is receiving at the time of enrollment or receives during the study must be recorded in the eCRF along with:

- Indication
- Dates of administration including start and end dates
- Dosage information including dose and frequency

DG participants enrolled in this study will likely consist mostly of patients receiving one or more prescription medications for blood-glucose control. Good clinical practice allows for frequent adjustment of medication by patients and their health care providers to minimize large fluctuations in glycemia, and this practice is encouraged in this study. It should be remembered that certain diabetic drugs (see [Table 7-2](#)) delay GE and are prohibited during this study. Other therapy considered necessary for the participant's welfare may be given at the discretion of the investigator. If the permissibility of a specific medication/treatment is in question, please contact the sponsor.

The sponsor or designee should be contacted if there are any questions regarding concomitant or prior therapy.

7.7.3 Rescue Medicine

Use of medications that may impact efficacy evaluations is strongly discouraged at any time after Visit 1 in the study. However, participants who experience severe symptoms of GP may receive a single day of treatment per week with an anti-emetic drug, but should avoid such treatment, if possible, during the 2-week Run-in Period, and on the day prior to and day of clinic visits during the Treatment Period. If a participant requires an anti-emetic drug (eg, 5-HT₃ receptor antagonists, NK1 receptor antagonists) for more than one day a week, or requires an anti-emetic drug once weekly repeatedly (ie, for 3 consecutive weeks or more), the investigator should contact the sponsor to discuss the safety of the participant continuing study treatment.

The date of rescue-medication administration as well as the name and dosage regimen of the rescue medication should be recorded in the concomitant medications page of the eCRF.

7.8 Treatment after the End of the Study

Participants who complete the study should follow up with the investigator regarding treatment at the end of the study.

8 Discontinuation/Withdrawal Criteria

Reasons for discontinuation from study treatment and/or the study may include the following:

- Adverse event
- Completed
- Death

- Failure to meet entry criteria
- Lack of efficacy
- Lost to follow-up
- Other
- Investigator decision
- Pregnancy
- Protocol deviation
- Site terminated by sponsor
- Study terminated by sponsor
- Withdrawal by participant

The reason for discontinuation should be clearly documented on the appropriate eCRF.

Discontinuation of study treatment also requires discontinuation from the study. (See [Appendix 8](#) for Standard Discontinuation Criteria/Definitions.)

8.1 Discontinuation of Study Treatment

Discontinuation of study treatment also requires discontinuation from the study. The following criteria should be evaluated:

- Special attention should be paid to the appearance of abnormal laboratory test results suggesting severe, drug-induced liver injury (DILI). Discontinuation of study treatment for abnormal liver function should be considered by the investigator when a participant meets criteria for Hy's law (see Section [9.2.7.1](#) and [Appendix 6](#)) or if the investigator believes that it is in best interest of the participant.

- ECGs should be carefully analyzed for findings pointing to potentially important cardiac events. If a clinically significant finding is identified (including, but not limited to changes from baseline in QT interval corrected using QTcB or QTcF after enrollment, the investigator or qualified designee should determine if the participant can continue in the study and if any change in participant management is needed. Generally, a QTc value of > 500 msec or an increase from baseline of > 60 msec after start of study treatment should prompt discontinuation of the participant from the study. Review of the ECG printed at the time of collection must be documented. Any new clinically relevant finding should be reported as an AE.
- Female participants who become pregnant during the study must be discontinued from treatment immediately and withdrawn from the study. See Section 9.2.5 and Appendix 5 for further details regarding follow-up of the participant through the pregnancy.

See the SoA (Section 2) for data to be collected at the time of treatment discontinuation.

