9.2.7 Adverse Events of Special Interest

9.2.7.1 Hy's Law

Study site personnel must report every participant who meets Hy's Law criteria, which are as follows:

- Alanine aminotransferase (ALT) or aspartate aminotransferase (AST) $\geq 3 \times$ upper limits of normal (ULN) AND
- Total bilirubin $\geq 2 \times$ ULN AND
- Alkaline phosphatase $< 2 \times$ ULN

Typically, all analytes will be obtained from the same sample, but they may come from multiple samples taken within a 24-hour period. This requirement applies from the time the participant signs the ICF for the study until 30 days after the final protocol-defined study visit or the last known dose of study treatment (if the final visit does not occur).

A laboratory alert for Hy's laws cases will be in place. Investigators and the sponsor must be immediately notified when the above criteria have been met. [REDACTED]

[REDACTED]
[REDACTED]
[REDACTED] Every effort to determine the cause of the liver enzyme abnormalities must be made, and close monitoring should be initiated in conjunction with the MSP and in accordance with the [FDA Guidance for Industry, Drug-Induced Liver Injury: Premarketing Clinical Evaluation, July 2009](#).

Additional details regarding liver safety assessments and follow up are provided in [Appendix 6](#).

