^b Details of liver chemistry stopping criteria and required actions and follow-up assessments after liver stopping or monitoring event are given in [Appendix 6](#).

^c Screening for drugs of abuse will be conducted using a urine drug screen at Visit -2.

Investigators must document their review of each laboratory safety report.

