12.6 Appendix 6: Liver Safety: Suggested Actions and Follow-up Assessments

Hy's law cases are considered AESIs. Hy's Law criteria are as follows:

- Alanine aminotransferase (ALT) or aspartate aminotransferase (AST) $\geq 3 \times$ upper limits of normal (ULN)
- AND Total bilirubin $\geq 2 \times$ ULN
- AND Alkaline phosphatase $< 2 \times$ ULN

Investigational product must be discontinued if any of the following criteria are met:

- ALT or AST $\geq 3 \times$ ULN and the participant is symptomatic with the appearance of fatigue, nausea, vomiting, right upper quadrant pain or tenderness, fever, rash, or eosinophilia ($> 5\%$)
- ALT or AST $\geq 3 \times$ ULN and total bilirubin $> 2 \times$ ULN or INR $> 1.5 \times$ ULN
- ALT or AST $\geq 5 \times$ ULN for more than 2 weeks
- ALT or AST $\geq 8 \times$ ULN

The participant may be re-challenged with study treatment only after consultation with the Allergan MSP. For participants who are not re-challenged with study treatment, the participant should be discontinued from the study and complete the Early Termination Visit. Participants should receive appropriate follow-up as per standard of care.

Hy's Law Cases

Sites must report every subject who meets the following Hy's law criteria if this occurs within the time the subject signs the ICF until 30 days after the last dose of study treatment.

A laboratory alert for Hy's laws cases will be in place, and the investigators and Allergan will be notified immediately when the above criteria have been met. Any Hy's laws case should be considered an SAE and also reported as an AE of Special Interest.

Every effort to determine the cause of the liver abnormalities must be made, and close monitoring should be initiated in conjunction with the Allergan medical monitor and in accordance with the FDA "[Guidance for Industry: Drug Induced Liver Injury - Pre-Marketing Clinical Evaluation](#)" July 2009.

12.7 Appendix 7: Medical Device Incidents: Definition and Procedures for Recording, Evaluating, Follow-up, and Reporting

Definitions of a Medical Device Incident

The detection and documentation procedures described in this protocol apply to all sponsor medical devices provided for use in the study (see Section 7.1 for the list of sponsor medical devices).

Medical Device Incident Definition

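### Protocol Section 8.1 leaves stopping study treatment at Hy's law to the investigator's consideration, while Appendix 6 makes it mandatory for every Hy's law case with total bilirubin above 2 × ULN

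*Protocol*

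**What the plan says.** Three parts of the protocol bear on a participant who meets Hy's law while on treatment.

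- **Section 8.1 (Discontinuation of Study Treatment).** "Discontinuation of study treatment for abnormal liver function should be considered by the investigator when a participant meets criteria for" Hy's law. The bullet refers the reader to Section 9.2.7.1 and Appendix 6. It adds, as an alternative ground, the investigator's view of the participant's best interest.
- **Section 9.2.7.1 and Appendix 6 (definition).** Hy's law is ALT or AST at or above 3 × ULN, with "Total bilirubin $\geq 2 \times$ ULN AND" alkaline phosphatase below 2 × ULN.
- **Appendix 6 (stopping rule).** "Investigational product must be discontinued if any of the following criteria are met". There are four criteria: ALT or AST at or above 3 × ULN with listed symptoms; "ALT or AST $\geq 3 \times$ ULN and total bilirubin $> 2 \times$ ULN or INR $> 1.5 \times$ ULN"; ALT or AST at or above 5 × ULN for more than two weeks; and ALT or AST at or above 8 × ULN.

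A footnote to Table 12-1 in Appendix 2 treats Appendix 6 as the authority: "Details of liver chemistry stopping criteria and required actions and follow-up assessments after liver stopping or monitoring event are given in" that appendix. Appendix 6 also says that a Hy's law case "should be considered an SAE and also reported as an AE of Special Interest".

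On leaving the study, Sections 8 and 8.1 say that anyone who stops treatment also leaves the study. Appendix 6 allows re-challenge after consultation with the medical safety physician and asks for study exit only where there is no re-challenge.

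**The concern.** Section 8.1 is where an investigator would look for stopping rules. Read alone, it presents the stop at Hy's law as something to weigh. An investigator who reads Appendix 6 finds an obligation for nearly the same set of participants. Section 9 allows no protocol waivers, so a site that kept a participant on treatment in reliance on Section 8.1 could be in breach of Appendix 6.

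Section 8.1 uses firmer verbs for other events. A pregnant participant "must be discontinued from treatment immediately and withdrawn from the study", and a QTc above 500 msec or a rise of more than 60 msec generally "should prompt discontinuation of the participant from the study". The QTc bullet also leaves room for judgement, so this comparison is supporting evidence only.

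What is at stake is a consistent safety stop for possible serious liver injury.

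**Working it through.** The plan gives no figure to reproduce. The check is whether meeting Hy's law implies a mandatory stop under Appendix 6, and in which cases.

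**Inputs** (multiples of ULN)

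- Hy's law, from Section 9.2.7.1 and Appendix 6: ALT or AST ≥ 3, bilirubin ≥ 2, alkaline phosphatase < 2.
- The overlapping Appendix 6 criterion: ALT or AST ≥ 3 and bilirubin > 2, or INR > 1.5.
- The other Appendix 6 criteria: ALT or AST ≥ 3 with symptoms; ≥ 5 for more than two weeks; ≥ 8.

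**Step 1: bilirubin above 2.** Hy's law supplies ALT or AST ≥ 3, and bilirubin > 2 is given. The overlapping criterion can be read in two ways:

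- ALT/AST ≥ 3 and (bilirubin > 2 or INR > 1.5): true, because both parts hold.
- (ALT/AST ≥ 3 and bilirubin > 2) or INR > 1.5: true, because the bracket holds.

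Alkaline phosphatase plays no part in the Appendix 6 trigger, so the Hy's law limit on it cannot take a case out. Every Hy's law case in this group must stop under Appendix 6, and Section 8.1 only asks the investigator to consider stopping the same participant.

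**Step 2: bilirubin exactly 2.** Hy's law holds, because its limit is ≥ 2, but the bilirubin limb of the stop trigger fails, because its limit is > 2. The case must still stop if there are listed symptoms, INR > 1.5, ALT or AST ≥ 5 for more than two weeks, or ALT or AST ≥ 8. If none applies, nothing in Appendix 6 compels the stop. An example is ALT 4, bilirubin 2.0, alkaline phosphatase 1, normal INR and no symptoms: Hy's law is met, with no mandatory stop.

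**Step 3: does the cross-reference settle it?** The Section 8.1 bullet sends the reader to Appendix 6, which holds both the definition and the stopping rule. It does not say that Appendix 6 prevails, and its own verb remains *consider*. The reader who follows it arrives at *must* with two instructions in hand.

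**Step 4: study exit and re-challenge.** The exit sentence in Sections 8 and 8.1 names no exception, while Appendix 6 provides one. Section 8.1.1 partly bridges the two. It allows a stop for an adverse event of up to three days, asks for sponsor contact if longer is needed, and contemplates restarting treatment. It does not mention liver stops, and Section 8.1.1 and Appendix 6 do not refer to each other. What is left is mainly a missing cross-reference.

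**Step 5: does the proposed threshold close the gap?** With the Appendix 6 trigger at bilirubin ≥ 2, any Hy's law case has ALT or AST ≥ 3 and bilirubin ≥ 2, so it meets the trigger by definition.

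**The case against.** The best contrary reading is that the two passages use *discontinue* differently. Section 8.1 opens by tying discontinuation to leaving the study, so what the investigator considers there may be permanent exit. Appendix 6 may instead mean an immediate stop, then a decision on re-challenge, with exit only if there is none. Both would then hold. The reading is coherent, but no sentence states it, and the Section 8.1 bullet speaks of study treatment.

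The safeguards are real. Section 8.1 cites Appendix 6. A laboratory alert notifies the investigator and the sponsor at once. The medical safety physician is involved. Section 9 asks that safety concerns be discussed with the sponsor immediately in deciding whether treatment continues. A site would be unlikely to decide alone. This lowers the practical risk but does not say which instruction applies.

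Part of Section 9.2.7.1, just after the notification sentence, is redacted and might hold further Hy's law instructions. The statement that nothing settles the matter is therefore limited to readable text. The title of Appendix 6 speaks of suggested actions, which may seem to soften it, but its stopping sentence is imperative and Appendix 2 calls the actions required. Classing Hy's law as an SAE governs reporting and does not show that treatment must stop.

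A reader might go further and infer that the protocol has no mandatory stop for Hy's law. Appendix 6 contains one. A reader might also infer that cases at exactly 2 × ULN are caught only through ALT or AST ≥ 8 × ULN. That would be so only if symptoms, raised INR and persistence were all absent.

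**Conclusion.** The inconsistency stands on the readable text. For every Hy's law case with total bilirubin above 2 × ULN, Section 8.1 says consider and Appendix 6 says must. At exactly 2 × ULN the mandatory list covers some cases and not others. The mismatch between the exit sentence and re-challenge is a lesser point that Section 8.1.1 partly covers.

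The conclusion assumes that *discontinue* has its ordinary meaning in both places and that the redacted part of Section 9.2.7.1 does not settle precedence.

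The documents give no expected number of Hy's law cases, so no count of affected participants is offered. It may be tempting to infer that sites kept Hy's law cases on treatment, or that the comparison between arms was affected. The documents support neither. The wording has no effect on power, error rate or bias. The SAP introduction records termination on 04 September 2020, so the point matters for the protocol as written and for any later protocol that reuses its text.

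**What to change.** - **Section 8.1.** Replace the Hy's law sentence with: *Study treatment must be discontinued when a participant meets Hy's law or any other Appendix 6 criterion, and may also be discontinued where the investigator judges this to be in the participant's best interest.*
- **Appendix 6.** For consistency, change the bilirubin trigger from > 2 × ULN to ≥ 2 × ULN, so that the stopping list and the Hy's law definition share one threshold. The Section 8.1 change alone would already cover the boundary case; this keeps the two places from diverging.
- **Sections 8 and 8.1.** After the exit sentence add: *except for MSP-approved re-challenge under Appendix 6.*

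The cost is protocol wording only: a clarifying amendment, or a correction before the text is reused. It needs no new visits, tests or data.

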8.1.1 Temporary Discontinuation

In the event of AE or intercurrent illness, dosing of study treatment can be stopped temporarily, for a maximum duration of 3 days. Should longer cessation of dosing be necessary, the investigator should contact the sponsor. The investigator should also contact the sponsor should either recurrence of the AE that prompted discontinuation or the appearance of a new AE that requires discontinuation be experienced after reintroduction of treatment to discuss the safety of this participant continuing study.

8.2 Withdrawal from the Study

- A participant may withdraw from the study at any time at his/her own request, or may be withdrawn at any time at the discretion of the investigator for safety, behavioural, compliance, or administrative reasons. An early termination visit must be performed as soon as possible after the decision to withdraw has been made by the participant or the decision to withdraw the participant has been made by the investigator.
- If the participant withdraws consent for disclosure of future information, the sponsor may retain and continue to use any data collected before such a withdrawal of consent.
- If a participant withdraws from the study, he/she may request destruction of any samples taken and not tested, and the investigator must document this in the site study records.
- See the SoA for data to be collected at the time of study discontinuation.

8.3 Lost to Follow Up

A participant will be considered lost to follow-up if he or she repeatedly fails to return for scheduled visits and is unable to be contacted by the study site.

The following actions must be taken if a participant fails to return to the clinic for a required study visit:

- The site must attempt to contact the participant and reschedule the missed visit as soon as possible and counsel the participant on the importance of maintaining the assigned visit schedule and ascertain whether or not the participant wishes to and/or should continue in the study.
- Before a participant is deemed lost to follow up, the investigator or designee must make every effort to regain contact with the participant (where possible, 3 telephone calls and, if necessary, a certified letter to the participant's last known mailing address or local equivalent methods). These contact attempts should be documented in the participant's medical record.
- Should the participant continue to be unreachable, he/she will be considered to have withdrawn from the study with a primary reason of lost to follow-up.

9 Study Assessments and Procedures

- Study procedures and their timing are summarized in the SoA (Section 2).
- Protocol waivers or exemptions are not allowed.
- Safety concerns should be discussed with the sponsor immediately upon occurrence or awareness to determine if the participant should continue or discontinue study treatment.
- Adherence to the study design requirements, including those specified in the schedule of activities, is essential and required for study conduct.
- The maximum amount of blood collected from each participant over the duration of the study, including any extra assessments that may be required, will not exceed 66.5 mL for rollover participants or 74.5 mL for de novo participants. Repeat or unscheduled samples may be taken for safety reasons or for technical issues with the samples.

9.1 Efficacy Assessments

[figure not shown]
9.1.1 Key Efficacy Assessment - DGSSD

[figure not shown]
The main efficacy assessment is the DGSSD, a 7-item, patient-reported diary designed to assess the severity of 6 core signs and symptoms of DG—nausea, abdominal pain, postprandial fullness, bloating, vomiting, and early satiety—and the frequency of vomiting episodes ([Appendix 13](#)). Participants will report their symptoms daily from Visit 1 to Visit 4 (Day 84) in the DGSSD. Thereafter, participants will report their symptoms daily for each of the 4 weeks preceding Visits 5, 6, and 7. DGSSD entries are to be made daily at the same time every evening on the electronic hand-held device throughout the Treatment Period. Planned periods for DGSSD entries are provided in the SoA ([Section 2](#)).

The severity of DG symptoms are assessed using a 0 to 10 numerical rating scale (NRS), on which 0 = “no” or “not at all uncomfortable” (ie, absence of the DG symptom) and 10 = “worst possible” or “most uncomfortable” (ie, worst experience of the DG symptom).

[figure not shown]
The overall assessment of the severity of non-vomiting symptoms is derived from the weekly DGSSS, as the sum of the weekly averages of the DGSSD items of nausea, abdominal pain, postprandial fullness, and bloating, calculated from a participant’s daily DGSSD responses.

The range of DGSSS is 0-40 with the worst possible DGSSS for the 4 DG symptoms being 40, and the best possible DGSSS being 0. Psychometric analyses have shown that a decrease in the DGSSS by ≥ 8 points and a decrease in individual symptom scores by ≥ 2 points is recognized as a clinically meaningful improvement in DG symptoms by affected patients ([Psychometric Evaluation, RTI Health, 2017](#)). Further psychometric analyses will be conducted to confirm the clinically meaningful thresholds for improvement.

Approval Date: 12-Feb-2021 17:35:16 (GMT)

Approval Date: 12-Feb-2021 17:35:16 (GMT)

9.2 Adverse Events

The definitions of an AE or SAE can be found in [Appendix 4](#).

AEs will be reported by the participant or noted by the investigator.

The investigator and any designees are responsible for detecting, documenting, and recording events that meet the definition of an AE or SAE and remain responsible for following up AEs that are serious, considered related to the study treatment or study procedures, or that caused the participant to discontinue the study treatment (see Section 8).

9.2.1 Time Period and Frequency for Collecting AE and SAE Information

All AEs and SAEs will be collected from the signing of the informed consent form (ICF) until 30 days after the final visit in the study (Visit 7) or Early Termination Visit at the time points specified in the SoA (Section 2). For rollover participants, ongoing AEs from lead-in Studies RLM-MD-01 and RLM-MD-02, and new AEs that occur after the signing of the ICF for RLM-MD-04 are considered to be AEs in RLM-MD-04.

Medical occurrences that begin before the start of study treatment but after obtaining IC (informed consent) will be recorded in the AE section of the eCRF and will be considered pretreatment AEs.

All SAEs will be recorded and reported to the sponsor or designee within 24 hours, as indicated in [Appendix 4](#). The investigator will submit any updated SAE data to the sponsor within 24 hours of it being available.

Investigators are not obligated to actively seek AE or SAE in former study participants. However, if the investigator learns of any SAE, including a death, at any time after a participant has been discharged from the study, and he/she considers the event to be reasonably related to the study treatment or study participation, the investigator must promptly notify the sponsor.

The method of recording, evaluating, and assessing causality of AE and SAE and the procedures for completing and transmitting SAE reports are provided in [Appendix 4](#).

